9.6.5 Overall Survival

The duration of OS will be measured from the time of first study drug administration until the date of death from any cause. Subjects who are known to be alive as of their last known status will be censored at their last date known to be alive. Subjects who are lost in follow-up will be censored at the date the subject is last known to have been alive. The censoring rules for OS are summarized [Appendix 14.5](#).

The summary of OS including the mean, minimum, maximum, median, Q1 and Q3 are provided for all the responders for each disease group.

Summary of 24 months K-M estimates of probability of OS including min, max, median and 95% CIs are provided for each group as well.

9.6.6 Analysis Methods

The analysis of DOR will be conducted on the subset of the All-treated Population who are defined as responder in protocol section 4.2. The analysis of PFS and OS will be conducted on the All-treated Population. The analysis of DOR, PFS, and OS will be estimated using the Kaplan-Meier (KM) method. KM estimates with 95% CIs will be calculated for event time quartiles, and event-free rates will be calculated at selected time points. In addition, the reason for censoring will be summarized for DOR, PFS and OS.

9.7 Analyses Safety Endpoints

Safety analyses will be performed on the All-treated Population.

9.7.1 Adverse Events

The Medical Dictionary for Regulatory Activities (MedDRA) will be used to code all AEs to a system organ class and a preferred term. The severity of the AE will be assessed by National Cancer Institute (NCI) Common Terminology Criteria for Adverse Events (CTCAE) Version 4.03 or higher. Drug-related AEs are those assessed by investigator as related.

Treatment-emergent AEs are defined as those events that occur (actual or imputed start date) on or after the first dose of study drug, through the treatment phase, and within 30 days following the last dose of study drug.

Treatment-emergent AEs will be summarized by system organ class and preferred terms in descending order of frequency, by NCI toxicity grade and by relationship to study drug. The same summary will be provided for serious treatment-emergent AEs and drug-related serious treatment-emergent AEs, treatment-emergent AEs leading to treatment discontinuation, dose reductions and dose withheld.

Death information is reported in the study exit CRF for all deaths. Incidences of deaths are to be reported, along with the primary cause of death.

AE by subject listing and death listing will be provided.

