# 5.4 MISSING DATA HANDLING

No imputation of values for missing data will be performed except that missing or partial start and end dates for AEs and concomitant medication will be imputed according to prespecified, conservative imputation rules. Subjects lost to follow-up (or drop out) will be included in statistical analyses to the point of their last evaluation.

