# 6.2.1 Adverse Event Reporting Period

After the signing of the ICF and prior to the first dose of study drug, all SAEs must be reported. After the first dose of study drug, all AEs/SAEs, irrespective of attribution of causality, must be reported.

For acalabrutinib, all AEs will be reported until 30 days after the last dose of acalabrutinib or the start of new anticancer therapy (whichever comes first). After this period, investigators should report SAEs or other AEs of concern that are believed to be related to prior treatment with acalabrutinib.

For pembrolizumab, all AEs must be reported through 30 days after the last dose of pembrolizumab; any SAEs, or follow-up to an SAE, including death due to any cause other than progression of the cancer under study, must be reported through 90 days after the last dose or 30 days after the last dose of pembrolizumab if the subject initiates a new anticancer therapy within the 90-day posttreatment timeframe.

SAEs considered related to study drug(s) or study procedures occurring after the end of the AE reporting period (as defined above) must be reported.

All AEs and SAEs that occur during the reporting period should be followed to resolution or until the investigator assesses the subject as stable, the subject is lost to follow-up or withdraws consent. Resolution/stable means the subject has returned to baseline state of health or the investigator does not expect any further improvement or worsening of the event.

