# 6.2.5 Expedited Reporting Requirements for Serious Adverse Events

All SAEs must be reported within 24 hours of discovery. All initial SAE reports and follow-up information will be reported using the protocol-specific electronic data capture system. If electronic SAE reporting is not available, paper SAE forms must be emailed or faxed to Acerta Pharma Drug Safety (see Table 12), or designee. These must also be completed within 24 hours of the discovery of the SAE. Acerta Pharma may request follow-up and other additional information from the investigator (e.g., hospital admission/discharge notes and laboratory results).

Whenever possible, AEs/SAEs should be reported by diagnosis term, not as a constellation of symptoms.

Death due to disease progression should be recorded on the appropriate form in the electronic data capture system. If the primary cause of death is disease progression, the death due to

disease progression should not be reported as an SAE. If the primary cause of death is something other than disease progression, then the death should be reported as an SAE with the primary cause of death as the event term, as death is typically the outcome of the event, not the event itself. The primary cause of death on the autopsy report should be the term reported. Autopsy and postmortem reports must be forwarded to Acerta Pharma Drug Safety, or designee, as outlined above.

If study drug is discontinued because of an SAE, this information must be included in the SAE report.

An SAE may qualify for mandatory expedited reporting to regulatory authorities if the SAE is attributable to the investigational product (or if a causality assessment is not provided for the SAE, in which case the default of 'related' must be used for expedited reporting purposes) and the SAE is not listed in the current acalabrutinib IB (i.e., an unexpected event). In this case, Acerta Pharma Drug Safety/Designee will forward a formal notification describing the suspected unexpected serious adverse reaction (SUSAR) to all investigators. Each investigator must then notify his or her IRB/IEC of the SUSAR.

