8 MISSING VALUES

No imputation of values for missing data will be performed except that missing or partial start and end dates for AEs and concomitant medication will be imputed according to prespecified, conservative imputation rules. Subjects lost to follow-up (or drop out) will be included in statistical analyses to the point of their last evaluation.

Imputation of partial dates will be made for AE onset and stop dates, start and end dates of concomitant medication, start date of subsequent anticancer therapy, date of initial diagnosis and death date. If dates are completely missing, no imputation will be made. For any partial date with missing year, no imputation will be made.

The general rule for imputation is:

- If only day is missing, then the 15th of the month will be used.
- If only year is present, then June 30th will be used.

If such imputation date for initial diagnosis is on or after date of first dose, the date of first dose – 1 will be used. If such imputed date for subsequent anticancer therapies is before date of last dose, the date of last dose + 1 will be used.

If the imputed date is for an AE start date and is in the same year and month as the first dose date but before the first dose date, then the first dose date will be used, or if the imputed AE start date is after the AE end date, then the AE end date will be used. If the imputed date is for an AE start date and is in the same year and month as but after the last dose date + 30 days, then the last dose date + 30 days will be used.

If the imputed date is for an AE end date and is after the death date, the date of death will be used, or if the imputed AE end date is before the AE start date, the AE start date will be used.

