9.5.2 Prior and Concomitant Medications Received for Indications Other than Target Disease

Data reported on concomitant CRF page will be used. Medications started or ended prior to first dose will be considered as prior treatment. Concomitant therapy is defined as all medications used on or after the first dose, through the treatment phase, and for 30 days following the last dose of study drug. Using this definition, a medication can be classified as both prior and concomitant. Start date and end date will be imputed based on the rules provided in Section **12.1.** of the SAP. Medications with completely missing start and stop dates will be considered as concomitant medications.

Prior and concomitant medications other than antineoplastic agents or other systemic therapies after enrollment will be summarized by the World Health Organization (WHO) Drug Dictionary therapeutic class, pharmacological class, and preferred term by each disease area.

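### An adverse event whose start date is completely missing or lacks the year can never enter the treatment-emergent tables, although the plan promises conservative imputation of missing AE dates

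*SAP*

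**What the plan says.** - **Definition.** SAP 9.7.1: "Treatment-emergent AEs are defined as those events that occur (actual or imputed start date) on or after the first dose of study drug", continuing to 30 days after the last dose. Entry to the tables depends entirely on a start date, recorded or imputed.
- **Promise.** Protocol 5.4 says that "missing or partial start and end dates for AEs and concomitant medication will be imputed according to prespecified, conservative imputation rules". SAP 8 opens with the same commitment.
- **Detailed rule.** Further down, SAP 8 says: "If dates are completely missing, no imputation will be made". It adds that a date lacking the year is not imputed either. If only the day is missing, the 15th is used; if only the year is known, 30 June is used. Two adjustments then pull an imputed AE start into the window: one in the month of first dose but before it becomes the first-dose date, and one in the month of last dose + 30 days but after that day becomes that day.
- **Medications.** SAP 9.5.2: "Medications with completely missing start and stop dates will be considered as concomitant medications".
- **Collection.** Protocol 6.2.1: "After the signing of the ICF and prior to the first dose of study drug, all SAEs must be reported". All AEs are reportable only from first dose.
- **Causality.** SAP 9.7.1: "Drug-related AEs are those assessed by investigator as related". No rule covers a blank entry.

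**The concern.** The detailed date rules undo the general promise. A reader of Protocol 5.4 would expect a fully missing AE start date to be handled in a way that does not flatter the treatment. Under SAP 8 and 9.7.1 together, such an AE gets no date, so it cannot meet the TEAE definition, and no fallback is offered. SAP 10 nevertheless reports no major change from the protocol's analyses.

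The tables affected carry the primary objective: TEAEs by system organ class, preferred term, grade and relationship, serious TEAEs, and TEAEs leading to discontinuation, dose reduction or withholding. An event lost from the TEAE set is lost from all of them. Exclusion is also the less plausible default for a non-serious AE, because before first dose only SAEs have to be reported.

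**Working it through.** The documents state no figure on this point, so the check is to trace one event through the rules and then bound the size.

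**Step 1. One event, five states of its start date.** The dates are illustrative, not from the documents: first dose 20 March 2016, last dose 5 September 2016. The window closes on 5 September + 30 days = 5 October 2016. The true AE start is 25 March 2016, inside the window.

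| What is recorded | Date after SAP 8 | In TEAE tables? |
|---|---|---|
| Full date | 25 March 2016 | Yes |
| Month and year | 15 March, moved to 20 March 2016 | Yes |
| Year only | 30 June 2016 | Yes |
| Day and month, no year | None | No |
| Nothing | None | No |

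The last two rows do not depend on the dates chosen. With no date, the condition in SAP 9.7.1 cannot be met.

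**Step 2. Direction.** For these two rows the rule never adds an event and always removes one that was truly treatment-emergent. The error can only be downward.

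**Step 3. Does this extend to missing AE dates in general?** No.
- *Day missing.* The two adjustments only bring events in. With the same dosing dates, a true start of 3 March (before first dose) becomes 20 March and is counted; a true start of 20 October (after the window) becomes 5 October and is counted.
- *Year only.* Errors go both ways. A true start of 15 January 2016 becomes 30 June and is wrongly counted. With first dose on 10 September 2016, a true start of 20 October 2016 becomes 30 June and is wrongly dropped.
- *Simulated check.* The rules were applied to 200,000 start dates. Assumptions, not from the documents: start uniform from 28 days before first dose to 90 days after last dose; first doses spread over about 2.4 years; 6 to 919 days on treatment. With the day missing, 0 of 159,284 true TEAEs were lost and 13,524 of 40,716 other events were added. With the year only, 29,830 true TEAEs were lost and 18,798 other events were added. The proportions depend on the assumptions; the directions follow from the rules.

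**Step 4. Size.** Protocol 5.1 gives 161 subjects. TEAE tables count subjects per row, so one affected subject moves a row by at most 1/161 = 0.0062, or 0.6 percentage points, and only if that subject has no other AE in that row. SAP 9.1 tabulates by nine disease types, whose sizes are not given. If they were equal (an assumption), 161/9 = 17.9 per group and the ceiling would be 1/17.9 = 5.6 points.

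**The case against.** **Such records should be rare.** Protocol 6.2.2 requires start and end dates for each recorded AE, and Protocol 7.4 requires complete case report forms. This stands, and it limits the size. It does not make the rule right for the cases that do arise.

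**The headline row will hardly move.** Protocol 1.4.2.1 reports that all 161 subjects already had at least one AE at the September 2017 cutoff. This also stands. Any effect would be in individual preferred-term, grade, serious and discontinuation rows.

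**The events are not hidden.** SAP 9.7.1 plans a by-subject AE listing. True, but a listing does not correct an incidence table.

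**After first dose is not the same as treatment-emergent.** Protocol 6.2.1 also collects SAEs between consent and first dose, SAEs to 90 days after pembrolizumab, and later related events. Setting undated events to the first-dose date would admit some of these and create false Day 1 onsets, while Protocol 3.1.1 lists timing of onset and duration as safety parameters. This stands and shapes the fix.

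**The medication rule is only an analogy.** SAP 9.5.2 applies when both start and stop dates are missing, and it concerns medications. It shows that the SAP knows how to write an inclusive default; it does not bind the AE rule.

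**On causality, a reader might infer that the SAP counts a blank entry as unrelated.** The documents do not say so. Read literally, such an AE would miss the drug-related tables, but the SAP states no rule, and a missing category is neither planned nor excluded. Protocol 6.2.5 does set a default for SAEs ("if a causality assessment is not provided for the SAE, in which case the default of" related applies), but only for expedited reporting, so it does not conflict with the descriptive tables.

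**Conclusion.** The point holds for one pattern. An AE whose start date is completely missing or lacks the year is always left out of the TEAE tables. That contradicts the commitment in Protocol 5.4 and in SAP 8's own first sentence. It is a stated rule with a wrong consequence, not just missing detail.

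For this pattern the bias can only be downward. Its size cannot be computed, because the number of such AEs is not given; it is probably small. The 0.6 points per affected subject is a ceiling that assumes 161 in the denominator and no other AE for that subject in the same row.

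A reader might go further and infer that missing data can only lower the primary safety counts. The documents do not support that. The day-missing rules can only raise TEAE counts, and the year-only rule can move them either way. Blank causality could affect only the drug-related tables, never the all-cause TEAE or serious TEAE counts, and the gap there is silence rather than a demonstrated error.

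**What to change.** Add to SAP 8, with a cross-reference in SAP 9.7.1:

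> An AE whose start date is completely missing or lacks the year is classified as treatment-emergent unless its end date or other recorded information shows that it ended before first dose, or began before first dose or more than 30 days after last dose. No onset date is assigned for timing or duration summaries. The number of AEs classified by this rule is footnoted.

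This classifies the event without inventing a date, so onset and duration summaries are untouched, and the exceptions cover both early and late events.

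The cost is one short rule, minor programming and a footnote. AE rates may become slightly less favourable, and a few events outside the window may be counted where nothing recorded shows it; the footnote lets the reader see how many are at issue.

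Optional clarification: state in SAP 9.7.1 how a blank causality entry is tabulated, for example as related in the drug-related tables, with a footnoted count.

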## 2.0 STUDY OBJECTIVES

## 2.1 PRIMARY OBJECTIVE

To characterize the safety profile of acalabrutinib and pembrolizumab in subjects with hematologic malignancies.

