#### All Parts

Treatment with acalabrutinib may be continued until disease progression or an unacceptable drug-related toxicity occurs as defined in the protocol. Treatment with acalabrutinib can continue until the end of trial, defined as 48 months after the last subject is enrolled. Subjects who are still on treatment at the end of the study and deriving clinical benefit from acalabrutinib treatment may be eligible to enroll in a separate rollover study of acalabrutinib monotherapy. In the event that a rollover or safety extension study is available at the time of the final data cutoff and database closure, subjects who remain in Study ACE-LY-005 may be transitioned to such a study. Once all active subjects are eligible for and move to a rollover or safety extension study would ensure treatment continuation, with visit assessments per the rollover or extension protocol. Any subject who would be proposed to move to a rollover or safety extension study would be asked to sign an Informed Consent Form (ICF) for the rollover or safety extension study.

Treatment with pembrolizumab may continue for 24 months (103 weeks) from first dose of pembrolizumab, provided subjects are tolerating the drug and not progressing. In addition, pembrolizumab treatment can end for subjects with confirmed CR (or sCR for MM) if treatment has been administered for at least 24 weeks and 2 doses of pembrolizumab have been administered after confirmation of CR/sCR. Subjects who have **confirmed** progressive disease will come off treatment. Note: If there is uncertainty regarding whether there is cancer progression, the subject may continue study treatment and remain under close observation (e.g., evaluated at 4- to 8-week intervals) pending confirmation of progression. In particular, transient worsening of disease during temporary interruption of study therapy (e.g., for drug-related toxicity or intercurrent illness) may not indicate disease progression. In such circumstances, and if medically appropriate, subjects may resume therapy and relevant clinical, laboratory, and/or radiographic assessments should be done to document whether tumor control can be maintained or whether actual disease progression has occurred.

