# 3.10.4 Transaminase Elevations for Acalabrutinib in Combination with Pembrolizumab

Serum transaminase elevations (including elevations of AST and/or ALT) may be increased in severity and frequency in subjects exposed to the combination of acalabrutinib and pembrolizumab, as compared with subjects exposed to pembrolizumab monotherapy and subjects exposed to acalabrutinib monotherapy. Routine monitoring for serum transaminase elevations must follow the Schedule of Assessments (serum chemistry laboratory assessments in Appendix 5 and Appendix 6). Dosing delays and modifications for subjects with serum transaminase elevations must follow guidance provided in Section 3.8.

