- aa All subjects continuing single-agent acalabrutinib treatment after Week 103 will have a Week 103 and Week 115 visit, and then every 24 weeks thereafter beginning at Week 127 through 3 years (for subjects with CLL/SLL histologies) or 5 years (for subjects with non-CLL/SLL histologies [i.e., DLBCL/Hodgkin lymphoma]), and then every 52 weeks thereafter (all histologies). Subjects who discontinue pembrolizumab at Week 103 must also have visits at Week 106 and Week 109. Subjects who discontinue pembrolizumab before Week 103 must continue visits every 3 weeks until Week 37, after which time visits are every 12 weeks through 104 weeks, and thereafter every 24 or 52 weeks as described above. However, it is noted that because the discontinuation timepoint of pembrolizumab (if applicable) is unique per subject, the first every 12-week visit for these subjects will be scheduled to align with the radiologic tumor assessment timepoint nearest to the 12-week interval.

									٦	Freatr	nent l	Phase	èp				Safety Follow- up Visit c	Follow -up Phase d
							We	eks						Wks 13-52	Wks >52		+30 days	Q12W
Study Weeks	Screening a	1	2	3	4	5	6	7	8	9	10	11	12	(Q3W)	(Q3W)	ET	after last dose	
Study Window	-28 days						1	±3 da	ys					±3 d	±3 d	+3 d	+7 d	±10 d
Informed consent	X																	
Confirm eligibility	х																	
Medical history	х																	
PE e /Vital signs f /Weight	х	Х	Х	х	Х	х	Х	х	Х	Х	Х	Х	Х	х	х	х	х	
ECOG status	х	х	х	х	х	х	х	х	х	х	х	х	х	x	х	х	х	
ECG g	х			1		1							İ 👘					
Lab assessments:						1												
Urine or serum pregnancy test h	x	x r,y			x			х			x			x	х			
Hematology (w/ smear) i	х	Xr	х	х	х	х	х	Х	х	х	х	х	Х	х	х	х	х	
Serum chemistry j	х	Xr	х	х	х	Х	Х	х	х	х	х	х	х	х	х	х	х	
Hepatitis serology z	Х																	
HBV PCR aa					Х				Х				х	Q4W	Q4W			Q4W
Thyroid panel k	Х	Xr	Х	х	Х	Х	Х	Х	Х	Х	Х	Х	х	Х	х	х	х	
Urinalysis i	х																	
CCI																		
Serum Ig n		xr					х							Wks 16 & 25, + Q9W	Q12W			
Disease markers o	х								As cli	nically	indic	ated						
Acalabrutinib 100 mg BID		Х	Х	Х	Х	Х	Х	Х	Х	Х	Х	Х	Х	Х				
Pembrolizumab 200 mg Q3W t								xt			xt			x t	x t			
Study drug compliance		х	х	х	х	х	х	х	Х	х	х	х	Х	Х	Х			
MRI/CT of spleen w	x							x						Wks 16 & 25, + Q9W	Q12W			

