6 ANALYSIS SUBSETS

6.1 All Treated Population

The safety analyses and primary efficacy analyses will be performed on the All-treated population, defined as all enrolled subjects who receive ≥ 1 dose of any study drug (either acalabrutinib or pembrolizumab).

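### SAP 9.7.1's single treatment-emergent window describes the whole regimen but cannot separate toxicity on the combination from events during later acalabrutinib-alone treatment

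*SAP*

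**What the plan says.** The primary objective (Protocol 2.1, repeated in SAP 2.1) is "To characterize the safety profile of acalabrutinib and pembrolizumab in subjects with hematologic malignancies". SAP 9.7.1 defines treatment-emergent events as those starting "on or after the first dose of study drug, through the treatment phase, and within 30 days following the last dose of study drug". SAP 6.1 treats a dose of either agent as a dose of study drug. The window therefore opens with the first dose of either drug and closes 30 days after the last dose of either.

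The two drugs have different planned durations (Protocol 3.0, All Parts). For pembrolizumab: "Treatment with pembrolizumab may continue for 24 months (103 weeks) from first dose of pembrolizumab". It may also stop sooner: "pembrolizumab treatment can end for subjects with confirmed CR (or sCR for MM) if treatment has been administered for at least 24 weeks" and two further doses follow confirmation. For acalabrutinib: "Treatment with acalabrutinib can continue until the end of trial, defined as 48 months after the last subject is enrolled". The single-agent phase is scheduled in its own right. Footnote aa to Protocol Appendix 5 says "All subjects continuing single-agent acalabrutinib treatment after Week 103 will have a Week 103 and Week 115 visit", with visits every 24 weeks and later every 52 weeks.

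SAP 9.7.1 tabulates events by MedDRA term, grade and relationship to study drug. It repeats this for serious events and for events leading to discontinuation, dose reduction or withholding. SAP 9.1 presents tables by disease type. SAP 9.7 contains no table by treatment period, no exposure-adjusted rate and no summary of time to onset, although Protocol 3.1.1 lists timing of onset and duration among the safety parameters. SAP 9.5.3 prints its acalabrutinib exposure sentence twice and never names pembrolizumab. Protocol 5.5.3 asks for both drugs.

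**The concern.** In Parts 1 and 2 both drugs start at Week 1, so the early part of the window is combination exposure. For a subject who continues acalabrutinib after pembrolizumab stops, the later part is not.

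The protocol itself treats the two phases differently. Section 3.10.4 warns that transaminase elevations "may be increased in severity and frequency in subjects exposed to the combination of acalabrutinib and pembrolizumab", compared with either drug alone. Appendix 5 sets different hepatitis B monitoring frequencies for combination treatment and for acalabrutinib alone. Visits thin out from every 3 weeks to every 24 or 52 weeks, so the intensity of event ascertainment changes too.

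In the planned tables, a first infection, second malignancy, atrial fibrillation or hemorrhage that arises a year after the last infusion enters the same cell as one in Week 4. A histology with durable disease control also accumulates more acalabrutinib-alone time than one that progresses quickly. Differences between the disease columns then partly reflect time on treatment. What is at stake is whether the report can say, in summary form, what happened while both drugs were being given.

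**Working it through.** **Inputs.**
- Protocol 3.0: pembrolizumab cap of 24 months (103 weeks); end of trial 48 months after the last enrolment.
- Protocol 5.1: enrolment closed in May 2017 with 161 evaluable subjects.
- Protocol 1.4.2.1, cut-off 3 September 2017: median exposure 3.4 months, longest 30.2 months; SAEs in 73 subjects; at least one AE in all 161.
- SAP version date: 17 January 2020.

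**Step 1, the plan's own figures.** 24 × 30.4375 / 7 = 104.4 weeks, against 103 stated (1.3% apart). 73/161 = 45.3%, as stated.

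**Step 2, length of the alone phase if pembrolizumab runs to the cap.**
- Last subject enrolled: 48 − 24 = 24 months, if dosing starts soon after enrolment.
- Longest-exposed subject: 30.2 months before 3 September 2017 puts the first dose no later than about 27 February 2015. From then to May 2021 is 74.1 to 75.1 months (1 or 31 May). Less 24, this leaves 50.1 to 51.1 months.
- Both are maxima, for someone still on acalabrutinib at the end of the trial. Counting 30 days after the last infusion as combination time shortens each by about one month. Stopping pembrolizumab early lengthens them.
- The SAP states no data cut-off. If the tables were cut at the SAP date, the figures would be 7.6 to 8.6 months and about 50.1 − 24.0 + 8.6 = 34.7 months.

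**Step 3, direction.** Crude incidence = subjects with at least one event / subjects treated. The denominator is fixed, and a subject once counted stays counted. Pooled incidence is therefore at least as high as combination-period incidence. Later follow-up can add subjects with events but cannot remove any. Any-grade incidence cannot move, since it was already 161/161.

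**Step 4, size for SAEs.** The documents give no split of exposure or events by period, so this is an illustration. Assume time on treatment is Weibull with the documents' median of 3.4 months and shape k (assumed). The share still treated past 24 months is S(24) = exp[−ln 2 × (24/3.4)^k]. Person-time shares use follow-up truncated at 48 or 75 months.

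| k | Share past 24 months | Of 161 | Person-time after 24 months |
|---|---|---|---|
| 1.0 | 0.8% | 1 | about 0.7% |
| 0.75 | 5.0% | 8 | 7.6% to 8.6% |
| 0.5 | 15.9% | 26 | 25% to 34% |

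Let a share f of subjects enter the alone phase, and let a proportion q of those still SAE-free (20% to 50%, assumed) have a first SAE in it. Pooled SAE incidence = 45.3 + f × 54.7 × q.
- f = 0.0075, q = 0.2: 45.3 + 0.1 = 45.4%.
- f = 0.05, q = 0.2 to 0.5: 45.8% to 46.7%.
- f = 0.16, q = 0.5: 45.3 + 4.4 = 49.7%.
- f = 0.30 (extreme), q = 0.5: 45.3 + 8.2 = 53.5%.

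**Limits of Step 4.** The 3.4 months is exposure up to the cut-off, and the protocol does not say to which drug. The last subjects enrolled had only 3.1 to 4.1 months of potential follow-up, so some exposures may be unfinished. The model counts only time past 24 months and so omits subjects who stop pembrolizumab early and continue acalabrutinib; their number is not given. Unfinished exposure and early stopping would both raise f. The 30% scenario allows for a larger f.

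**The case against.** The strongest reply is that the regimen under study is the whole sequence: both drugs, then acalabrutinib alone. The primary objective names two drugs, not a period of concurrent dosing. A window from first dose to last dose plus 30 days, in all treated subjects, describes that sequence. This stands. A reader might infer that the AE rates do not describe the combination at all, and the documents do not support that. Both drugs start together. Half the subjects had no more than 3.4 months of exposure by September 2017, so any alone phase within that time was short.

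Two other readings are tempting. One is that combination-specific events, such as transaminase elevations, are diluted by follow-up without pembrolizumab. Step 3 rules this out for the per-subject percentages that the SAP plans; dilution would need person-time rates pooled over both phases. The other is that about two thirds of exposure is acalabrutinib alone (50.1/74.1 = 0.68). That is one subject, assumed to stay on treatment to May 2021.

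There are also mitigations. Events are summarised by relationship to acalabrutinib, pembrolizumab or both (Protocol 5.5.1, SAP 4.1). Discontinuation is reported per drug (SAP 9.2). Subject-level AE listings (SAP 9.7.1) and laboratory plots over time (SAP 9.7.2) are planned. SAP 5 tests no hypothesis. These soften the gap without closing it. Attribution is investigator judgement in an open-label single-arm study and does not record whether pembrolizumab was being given. A listing is not a summary. SAP 9.6.1.2 plans an alone-versus-combination description for response, but it splits subjects rather than time and has no safety counterpart.

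Finally, Protocol 3.8.2 notes that immune-related events can appear months after the last pembrolizumab dose. Resting the safety conclusion on the combination period alone would be less conservative than the pooled window. That objection also stands, and the fix respects it.

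**Conclusion.** The point holds as a reporting gap that bears on the primary objective. It is not an error in the pooled tables. Those tables give a valid account of the regimen but cannot isolate what arose while pembrolizumab was being given, because the window includes an alone phase that can last from about 24 to about 50 months for subjects who reach the cap.

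The effect on crude incidence is upward only. For SAEs overall it is probably small: about 0.1 to 4.4 percentage points, with 8.2 as an extreme. That range rests on an assumed Weibull shape, an assumed 20% to 50% chance of a first SAE in the alone phase, and the same SAE-free share among subjects who enter that phase as among all subjects. The effect falls mainly on late-onset events and on histologies with long treatment, where a small overall shift can hide a larger one in a single disease column. It is a cheap improvement worth making.

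**What to change.** In SAP 9.7.1, keep the pooled full-regimen tables as the main summary. Add supplementary tables of TEAEs, SAEs, Grade ≥3 events and discontinuations, with person-time and exposure-adjusted rates, for two periods:

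1. Combination: first dose through 30 days after the last pembrolizumab dose.
2. Acalabrutinib alone: from then through 30 days after the last acalabrutinib dose.

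Use the same boundary for AEs and SAEs, so that one event cannot fall in different periods in different tables. State how subjects who stop acalabrutinib first are assigned. Add a sensitivity version with the boundary at 90 days after the last pembrolizumab dose, or 30 days if new anticancer therapy starts, to match the SAE collection rule in Protocol 6.2.1. Say how days 31 to 90 are handled in subjects who stop both drugs together, because SAEs are still collected then but fall outside the 30-day window.

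Draw the primary safety conclusion from the pooled and by-period tables together. Correct SAP 9.5.3 so that pembrolizumab exposure is reported, as Protocol 5.5.3 requires.

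The cost is SAP wording and one extra set of tables from dose and AE-onset dates already collected. Treatment and data collection do not change. The small downside is that some late immune-related events will fall in the second period; a footnote and the attribution column should flag them.
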